#### 3.4.7 Targeted follow-up

If one or more major or minor malformations are noted, it may be necessary to collect additional information. Signed release forms will be obtained by the enrolling HCP from the mother to acquire maternal and pediatric medical records and permission to contact the appropriate HCP, i.e., obstetrician/gynecologist, and/or pediatrician. Medical records will

allow for case verification. Each potential case will undergo clinical review to confirm status as a congenital anomaly case and to ensure the anomaly (or anomalies) are coded appropriately (i.e., accurately represent the defect or underlying diagnosis). Many terms are used clinically for the same structural or functional defect; therefore, the coding and grouping of anomalies is the key to a meaningful analysis of results. The clinical reviewer will determine what, if any, structural or functional abnormalities are present, if these are minor or major malformations and if there is additional information required to assess the case (e.g., pathology reports, medical records, assessment by neonatologist/pediatrician).

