## 5 Statistical analysis

#### 5.1 Statistical methods

Descriptive statistics will be used to summarize the findings; specifically, overall frequency (proportion, 95% confidence interval) of major malformations will be calculated, as well as frequencies of specific outcomes, e.g., heart defect, spina bifida, club foot deformity, cleft palate. The same will be calculated for minor congenital malformations, spontaneous abortions, stillbirths, elective terminations, adverse effects on immune system development, and any other adverse pregnancy outcomes. Minor anomalies will be grouped and reported as "defects case", if three or more occur in the same child. All primary analyses will be restricted to prospectively identified cases with outcome information available. Retrospectively identified cases (refer to Section 3.1 for description) will be collected and analyzed; however, these cases will not be included in any outcome rates calculated for the primary analysis. Multiple and singleton gestations will be presented separately.

The frequency of major malformations in the proposed registry will be compared to the frequency of major malformations in infants in the external comparison groups, i.e., MACDP (CDC) for US data, EUROCAT for European cases and data collected by external investigators including data made available from other registries that include pregnancy exposure and outcome information. Furthermore, using an internal comparison approach (if enough data is available), the risk of congenital anomalies among women with first trimester exposure will be compared with risks of congenital anomalies among women with second and third trimester exposure to investigate if there is an increased risk (risk estimate, 95% confidence interval) of major malformations among infants exposed to fingolimod.

In order to assess the overall generalizability and representativeness of the data included in this registry demographics of the registry population and the population of all pregnancy cases reported to pharmacovigilance will be summarized.

[figure not shown]

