## 5.2 Sample size determination

In the US 3,030 infants with birth defects per 100,000 live births were reported by CDC (2010). The European surveillance of congenital anomalies (EUROCAT) reported a prevalence rate of 2334.2 per 100,000 live births (EUROCAT 2010). Worldwide about 6% of all newborn infants have serious birth defects of genetic or partially genetic origin and the annual prevalence of congenital malformations was 3,650 per 100,000 births (Christianson et al 2006).

The following chart (Figure 5-1) shows the power of this registry based on different numbers of women included to detect at least a 50% to 100% increased risk of any major malformation. Based on this assumptions the study will have >80% power (two-sided test,  $\alpha$  set at 0.05) to detect a 80% risk increase if 500 women are included assuming a background prevalence of major malformations of 3% (nQuery Advisor 5.0).

Although it is expected that up to 500 women may potentially be enrolled during the at least four year recruitment period of the study, the rate of enrollment will not be known until actual accrual of patients begins (for details for the reasons for discontinuing this pregnancy registry refer to Section 3).

Figure 5-1 Power based on number of included women (N) to detect a 50% to 100% risk increase based on a background prevalence of 3%

Although designed primarily as a prospective registry, the registry will accept retrospective reports of pregnancy outcome, meaning cases initially reported to the registry after the outcome is known. Similar to passive spontaneous case reporting, these reports may contribute to the differential reporting of poor outcomes but may also provide important information. The registry will allow for retrospective reports to be differentiated from prospective reports and analysis will be done separately. Although these cases do not contribute to the evaluation of true event rates in the exposed population, these cases may still provide important information.

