Structural and functional congenital anomalies identified in the perinatal period through one year of age will be collected and classified. The registry will utilize congenital anomaly definitions and classifications consistent with the MACDP and the EUROCAT surveillance programs (i.e., ICD9 or ICD10-BPA), to the extent possible, in order to facilitate comparisons (details regarding coding and classification, and case definition, will be established in registry-specific clinical review procedures). Both coding methods will be utilized.

Chromosomal abnormalities (and genetic disorders) will be evaluated separately due to the low likelihood that these defects would be associated with drug exposure. Defects identified outside of the study period may also be reported to the registry, but it is not the intention of the registry to pursue long-term data (> one year) regarding the offspring. All congenital anomalies reported will be reviewed periodically by a clinical reviewer who will determine whether additional follow-up with the reporting physician is required in order to classify the event (including classification into minor or major anomalies), and will review the coded datasets overall for accuracy and internal consistency. The calculation for risk of congenital malformations will be made by dividing the number of congenital anomalies associated with any pregnancy outcome by the sum of the number of live births without congenital anomalies and any outcomes involving congenital anomalies. Estimates of risk will also be analyzed as stratified by trimester of exposure.

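### The section 5.3 risk formula counts anomalies in the numerator and outcomes in the denominator, so as written it does not give the proportion that section 5.1 requires

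*Protocol*

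**What the plan says.** The protocol gives one explicit calculation of malformation risk. It stands in the text on classification of exposures and outcomes (listed as section 5.3 in the table of contents), after the sample size text. The risk is obtained by "dividing the number of congenital anomalies associated with any pregnancy outcome by the sum of the number of live births without congenital anomalies" and the outcomes that involve anomalies; the full denominator reads "live births without congenital anomalies and any outcomes involving congenital anomalies". The same calculation is then to be stratified by trimester of exposure.

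Other passages bear on the unit of counting:

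- Section 5.1 sets the primary summary: "overall frequency (proportion, 95% confidence interval) of major malformations will be calculated". It gives no numerator or denominator.
- Section 5.1 groups minor anomalies into a single defects case "if three or more occur in the same child". It has no corresponding rule for major malformations.
- Section 3.4.7 has a clinical reviewer check each potential case "to ensure the anomaly (or anomalies) are coded appropriately", so more than one anomaly per case is foreseen.
- Section 5.2 gives the US reference per infant: "In the US 3,030 infants with birth defects per 100,000 live births were reported by CDC (2010").
- Section 5.3 leaves part of the matter to another document: "details regarding coding and classification, and case definition, will be established in registry-specific clinical review procedures".

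**The concern.** The two parts of the ratio are in different units. An infant with a septal defect and an unrelated renal defect enters the numerator twice and the denominator once. The numerator is then not a subset of the denominator. The ratio is not a proportion, it could exceed 1 in a small trimester stratum, and a binomial interval does not describe its uncertainty.

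The direction of any error is fixed: the ratio can equal the affected-outcome proportion or exceed it, but never fall below it. The registry frequency is to be set against surveillance rates, and section 1 describes a narrow contrast: about 5% in post-marketing reports against 2 to 4% in the general population. A modest upward factor matters on that scale, because the results are meant for counselling patients.

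**Working it through.** **Inputs from the protocol (section 5.2).** Up to 500 women, 3% background, an 80% increase (3% × 1.8 = 5.4%), two-sided α = 0.05, stated power above 80%.

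**Input not in the protocol.** The mean number of anomalies per affected outcome, *m*. I assume 1.0 to 1.5 and show the range.

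**Step 1: the plan's own figure.** One-sample test of a proportion against a fixed 3%, normal approximation:

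Φ[(0.024 × √500 − 1.96 × √(0.03 × 0.97)) / √(0.054 × 0.946)] = Φ[(0.5367 − 0.3344) / 0.2260] = Φ(0.895) = 81.5%.

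This agrees with the stated power. The calculation treats the endpoint as one yes/no result per unit, which is the counting unit that section 5.3 departs from.

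**Step 2: what the formula returns.** Let *A* be the number of affected outcomes and *D* the denominator. The formula gives (*A* × *m*) / *D* = (*A* / *D*) × *m*. With *D* = 500:

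| *m* (assumed) | 15 affected (3.0%) | 27 affected (5.4%) |
|---|---|---|
| 1.0 | 3.0% | 5.4% |
| 1.05 | 3.15% | 5.67% |
| 1.1 | 3.3% | 5.9% |
| 1.2 | 3.6% | 6.5% |
| 1.5 | 4.5% | 8.1% |

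A true 3% would be reported as 5.4%, the full increase used in the power statement, at *m* = 5.4 / 3 = 1.8.

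**Step 3: an illustrative consequence.** Suppose that an excess is declared when the exact (Clopper-Pearson) lower 95% limit is above 3%. With 500 outcomes this needs a count of at least 24: the binomial upper tail at 3% is 0.0306 for 23 and 0.0179 for 24, and the tail must be below 0.025. Take a true risk of 3%, and let a share *s* of affected outcomes have two anomalies and the rest one, so that *m* = 1 + *s*:

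| *m* (assumed) | Chance that the lower limit exceeds 3% | Coverage of 3% |
|---|---|---|
| 1.0 | 1.8% | 96.5% |
| 1.05 | 3.6% | 95.0% |
| 1.1 | 6.1% | 92.8% |
| 1.2 | 13.0% | 86.3% |
| 1.5 | 41.6% | 58.1% |

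At *m* = 1.2, allowing some outcomes three anomalies (probabilities 0.85, 0.10 and 0.05 for one, two and three) gives 13.7% and 85.5%. The mean drives the result; the exact distribution matters little.

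**Step 4: units side by side.** The US figure of 3,030 per 100,000 is a count of infants. The EUROCAT figure of 2334.2 per 100,000 live births is given without saying whether infants or anomalies are counted. A mismatch of units is therefore shown for the US comparison only.

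**The case against.** The strongest reply is that affected outcomes were plainly intended. Section 5.1 asks for a proportion. The denominator divides outcomes into those with and without anomalies, the usual layout for affected over evaluable. Section 3.4.7 confirms each report as a congenital anomaly case, and case definition is deferred to clinical review procedures. The rule on three or more minor anomalies is itself a per-child grouping. Coding to the underlying diagnosis could merge related defects into one.

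Most of this stands, and it limits the finding. A reader might infer that the primary frequency will be overstated and that a drug without effect will appear harmful. The documents do not support that: the inflation arises only if the formula is applied literally and some outcomes carry more than one counted anomaly, and the number per outcome is not given. A reader might also infer that the roughly 5% in section 1 is inflated in this way, but nothing says that it was produced with this formula. The 500 outcomes in the working are a ceiling (260 patients were enrolled at Amendment 3), and section 5.1 describes a descriptive summary, not a signal rule.

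The reply does not rescue the sentence itself. Two unrelated major malformations in one infant are covered by no grouping rule. Deferring coding and case definition does not amend a calculation that the protocol fixes. Nor is this a detail left to an analysis plan: the protocol states the calculation, and a plan that counted infants would depart from it.

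**Conclusion.** The numerator in section 5.3 is misworded and conflicts with section 5.1. Used as printed, the formula returns the affected-outcome proportion times the mean number of anomalies per affected outcome, and it is not comparable with the infant-based US figure.

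The bias is upward or zero. Its size rests wholly on an assumed mean: negligible near 1.0, 0.3 percentage points on a true 3% at 1.1, and 1.5 points at 1.5. The false-excess chances additionally assume 500 outcomes and a decision rule that the protocol does not contain. The wording is certain; the inflation is conditional. A correction is still warranted, because this is the only stated formula and it also governs the trimester strata.

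**What to change.** Change only the numerator in section 5.3, to the number of outcomes (infants or fetuses) with at least one qualifying malformation, each counted once and in the same unit as the existing denominator. Then:

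- use that unit in the trimester strata and in the external comparisons, and state the unit of the EUROCAT rate used;
- in type-specific rates, count an infant once per type;
- report the number of anomalies per affected infant descriptively.

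Leave the composition of the denominator as it is. Replacing it with a broader evaluable set could admit losses without anomalies, which is a different question. Leave the separate presentation of multiple and singleton gestations as it is too.

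The cost is one phrase in the protocol and a matching line in the analysis specification. No new data are needed, since malformations are recorded for each infant. The stated power is unchanged, because it already assumes one yes/no result per unit.

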## 3.4.5 One-year follow-up (infant age 10 to 14 months)

The following data will be collected at one-year follow-up for each infant:

- Date of contact
- Any major or minor malformation(s) diagnosed since initial birth report.
- Infant vital status (alive / deceased).
- Infant height, weight and head circumference.
- History of significant diseases, including any requiring hospitalization and medications.
- Relevant testing/procedures performed and any associated diagnoses (if a specific diagnosis is not possible or available, the results/findings of the testing should be reported for completeness).
- Potential adverse effects on immune system development (e.g., serious infections requiring hospitalization).
- Breastfeeding history and duration (months).
- Developmental milestone status.
- Other relevant testing/procedures performed and any associated diagnoses.

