#### 3.4.8 Lost to follow-up

Registry pregnancy reports will be considered complete for live births when data regarding the pregnancy, neonatal and infant outcomes through one year have been received. For pregnancies that do not result in a live birth, follow-up is complete once pregnancy outcome details have been provided.

At enrollment (and as part of the informed consent process), patients will be asked to provide their contact details as well as the contact details of at least two other people (e.g., a family member or a friend living outside of the patient's home), in case the patient is not reachable and an alternate contact is needed. Patients will be contacted by email (if provided), then by telephone. If the patient cannot be reached by these modalities, then the alternate contact(s) will be contacted by the registry site.

For registry purposes, patients will be considered lost to follow-up if any time-based assessment is missed and the corresponding data have not been received by the registry after making additional follow-up attempts using all contact modalities available (e.g., phone, fax, registered receipt letter). At least 3 attempts will be made up to 4 months after the expected date of the missed assessment. Patients will be considered lost to follow-up 30 days after the last contact attempt. The case will be re-opened should additional information be later obtained. All HCPs on record will be contacted prior to considering the patient lost to follow-up. All data collected prior to considering the patient lost to follow-up will be used for analysis and reporting purposes, to the extent possible. The date of discontinuation is considered the date of the last successful contact with the patient.

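### The malformation risk counts anomalies found through one year but sets no follow-up condition for a live birth to enter the denominator as anomaly-free

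*Protocol*

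**What the plan says.** Three parts of the protocol bear on which infants are evaluable.

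- **Section 5.3 (classification of exposures and outcomes)** sets the window: "Structural and functional congenital anomalies identified in the perinatal period through one year of age will be collected and classified". The numerator of the risk is a count of anomalies over all types of pregnancy outcome. The denominator is the "sum of the number of live births without congenital anomalies and any outcomes involving congenital anomalies". No minimum follow-up is attached to a live birth without an anomaly.
- **Section 3.4.8 (lost to follow-up)** says of registry pregnancy reports that they "will be considered complete for live births when data regarding the pregnancy, neonatal and infant outcomes through one year have been received". It also says: "All data collected prior to considering the patient lost to follow-up will be used for analysis and reporting purposes, to the extent possible". Section 3.1.2 likewise retains what was collected before a withdrawal.
- **Section 5.1 (statistical methods)** restricts the primary analyses to prospective cases whose outcome information is available. It does not say whether, for a live-born infant, this means the pregnancy outcome or the one-year outcome.

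Late diagnoses are expected. The one-year form in Section 3.4.5 asks for "Any major or minor malformation(s) diagnosed since initial birth report", and Section 3.4.4 asks the same at the three-month follow-up (infant age 3 to 9 months). Section 3.4.9 names a high rate of loss to follow-up as a possible reason to end the registry.

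**The concern.** The numerator can grow until the first birthday, but an infant can enter the denominator as a non-case on the strength of the birth report alone. The protocol's own completeness rule treats such a record as incomplete, while the risk formula does not distinguish it from a full year of observation. A malformation that would have been diagnosed after contact was lost is then scored as absent.

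This matters because the malformation frequency is the primary objective, is to be compared with external surveillance data, and is meant to inform counselling (Section 2). Late diagnoses missed in this way push the one-year risk towards reassurance, by an amount that rises with loss to follow-up.

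**Working it through.** **The plan's own figure.** Section 5.2 claims more than 80% power, two-sided α 0.05, for an 80% increase over a 3% background with 500 women. The target risk is 1.8 × 3% = 5.4%. With a one-sample normal approximation:

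- Standard error at 3%: √(0.03 × 0.97 / 500) = 0.00763
- Standard error at 5.4%: √(0.054 × 0.946 / 500) = 0.01011
- Power = Φ[(0.054 − 0.03 − 1.96 × 0.00763) / 0.01011] = Φ(0.895) = 81.5%

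The stated figure reproduces under this method.

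**The component in question.** Let p be the true one-year risk, s the share of malformations first diagnosed after the birth report, and L the share of live births lost after that report. Assume that loss is unrelated to outcome. Cases seen are those found by the birth report, p(1 − s), plus later ones in infants still followed, p·s(1 − L). If lost infants count as anomaly-free:

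observed risk = p(1 − s) + p·s(1 − L) = p(1 − L·s)

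The relative understatement is L·s. Neither L nor s is in the protocol; both are assumed at 10–40%. With p = 5.4%:

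| L | s | Observed risk | Relative change | Power at n = 500 against 3% |
|---|---|---|---|---|
| 10% | 10% | 5.35% | −1% | 80.1% |
| 20% | 30% | 5.08% | −6% | 72.3% |
| 30% | 30% | 4.91% | −9% | 66.8% |
| 40% | 40% | 4.54% | −16% | 51.7% |

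The power column is illustrative. It takes the 3% background as a risk fully ascertained to one year, which the protocol does not state.

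**Infants seen later than birth.** L here means infants last seen at the birth report. For an infant last seen at the 3–9 month contact, only malformations first diagnosed after that contact are missed, so a smaller s applies. Using all infants without one-year data as L, together with all post-birth diagnoses as s, would overstate the effect.

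**Two tempting repairs that fail.**

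1. *Drop only the anomaly-free lost infants and keep known cases.* The risk becomes p(1 − L·s) / [p(1 − L·s) + (1 − p)(1 − L)]. At L = 20%, s = 30%: 0.05076 / (0.05076 + 0.7568) = 6.29%, which is 16% too high.
2. *Keep only live births followed to one year, plus all non-live outcomes with an anomaly.* Take an assumed 500 evaluable outcomes with 27 cases, 5 of them terminations, and 30% of live births lost. Then (22 × 0.7 + 5) / (495 × 0.7 + 5) = 20.4 / 351.5 = 5.8%, against 27 / 500 = 5.4%.

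**Censoring at last contact.** Take L = 20%, s = 30%, all loss just after the birth report. The risk at birth is 5.4% × 0.7 = 3.78%. Among the remaining 96.22%, the later risk is estimated in the 80% still followed: (1.62% × 0.8) / (96.22% × 0.8) = 1.684%. The cumulative risk is 1 − 0.9622 × (1 − 0.01684) = 5.40%, which recovers the true value.

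**The case against.** The strongest objection is that the protocol nowhere says outright that lost infants count as anomaly-free. Section 5.1's restriction could be read with Section 3.4.8's completeness rule so as to exclude them, Section 3.4.8 uses partial data only as far as possible, and an SAP may settle the matter. It stands that this handling is an inference, though the most natural one: the retention rules and the formula point the same way. The point does not rest on the SAP's absence, because the protocol itself fixes both the formula and the retention of partial records. Nor does the stricter reading remove the difficulty, since exclusion can bias the risk upward, as shown above.

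A reader might also infer that the primary malformation risk as a whole is biased downward. The documents do not support that. The same formula counts anomalies rather than affected infants, and it leaves out losses and terminations without an anomaly while including those with one. Both push the figure up. They are separate features and cannot be relied on to cancel this one, but the net direction is unknown.

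Nor can a bias against MACDP or EUROCAT be claimed. The protocol does not give their ascertainment windows, and some of the effect would cancel if their follow-up were incomplete in the same way.

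Finally, the protocol works to limit loss: alternate contacts, at least three attempts, contact with all health care providers, a contact at about six months where regulations allow, and data collection at discontinuation. These reduce L and shorten the unobserved period; they do not set a rule for infants who are still lost.

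**Conclusion.** The point holds in limited form. Sections 3.1.2, 3.4.8, 5.1 and 5.3 do not together define one evaluable infant, and on the most natural reading an infant lost after the birth report is scored as anomaly-free for the whole year. Taken alone, this can only lower the one-year risk. The size is L × s: about 1–16% in relative terms when both are assumed to be 10–40%, so a true 5.4% appears as 5.35% to 4.54%. It rests on those assumed ranges and on loss being unrelated to outcome. It is small if loss is low or most malformations are recognised at birth. Separate estimates with stated follow-up would answer the registry's question better than the single formula.

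**What to change.** In Section 5.3, replace the single formula with two risks, each counted per affected infant or fetus:

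1. **Post-partum-window risk.** Malformations identified by the end of the post-partum window, over live births with a post-partum report plus other outcomes with an anomaly.
2. **One-year cumulative risk.** A Kaplan-Meier estimate through one year, with live-born infants censored at last contact and non-live outcomes with an anomaly counted as events at time zero. State its assumption that loss is unrelated to later diagnosis.

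Show the number of infants followed at each time point. Define in Section 5.1 what available outcome information means for an infant, to match each estimate. State which estimate is set against each external reference. Do not use the completers-only version, and do not drop only the anomaly-free lost infants.

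The cost is a change of wording, one extra table and a somewhat wider interval for the one-year estimate. The follow-up forms already record the date of contact.

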There is currently no evidence that MS itself is associated with an increased risk of adverse pregnancy outcomes (i.e., miscarriage, stillbirth or congenital malformations, details see Dahl et al (2005), Dahl (2008), Dahl et al (2008), Kelly et al (2009) and Houtchens (2007), therefore comparison data from large surveillance systems or national statistics should allow a valid comparison. Furthermore, as the highest risk for major malformation is related to exposure during the first trimester, the frequency of congenital malformations among women with first trimester exposure will be compared to women with second and third trimester exposure (if sufficient data are available) to allow an additional internal comparison. Relevant published data sources will be used to evaluate the frequency of other adverse pregnancy outcomes in the exposed population.

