Prenatal exposure will be summarized by trimester(s) exposed as well as exposure up to 8 weeks before LMP, dose and regimen. Exposures at specific gestational ages (in weeks) will be evaluated for individual cases. Exposure to other drugs and biologics will be collected, and HCPs will be able to indicate if there is a suspected, probable or known cause for any adverse pregnancy outcome. Trimesters will be defined as < 14 weeks (1st trimester), 14 to 27 weeks (2nd trimester) and  $\ge 28$  weeks (3rd trimester).

Spontaneous pregnancy loss will be defined as pregnancy loss at < 20 weeks gestation. Gestational age corrected by ultrasound will be used for gestational age when available, otherwise gestational age based on LMP will be used. Stillbirth (fetal death) will be defined as any pregnancy loss at  $\ge 20$  weeks gestation.

Low birth weight (LBW) is defined as < 2500 grams (5 pounds, 8 ounces) at birth and very low birth weight (VLBW) is defined as < 1500 grams (3 pounds, 4 ounces). Intrauterine growth retardation (IUGR) will be defined as estimated fetal weight below the 10th percentile for gestational age. It is important to note, however, that as many as 70% of fetuses who are estimated to weigh below the 10th percentile for gestational age are small simply due to constitutional factors such as female sex or maternal ethnicity, parity, or body mass index (Manning 1995). This definition covers all small for gestation fetuses and does not make a distinction among fetuses who are constitutionally small, growth restricted and small, and growth restricted but not small; therefore, any report of IUGR in the exposed population will require further assessment to ensure the case is appropriately categorized. In addition, cases where the physician has reported decreased relative growth even though the infant is > 10th percentile, may be included in the overall analysis of potential in-utero growth restriction. Moderate and severe IUGR will be defined as fetal weight in the 3rd to 10th percentile and less than 3rd percentile, respectively (Peleg et al 1998). For infants, the same criteria (i.e., weight below the 10th percentile for gestational age) will be applied but referenced as small for gestational age (SGA) at birth. An infant who is larger than expected for the age and gender, with a birth weight above the 90th percentile, will be considered large for gestational age (LGA).

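### The trimester-stratified malformation risk favours later exposure by construction, because anomaly-affected pregnancies that end early can count only in the earlier stratum

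*Protocol*

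**What the plan says.** The relevant rules are in the Protocol, in Sections 3.5 and 5.1 and in the classification text after the sample size (Section 5.3 in the table of contents).

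- **Risk formula (5.3).** The risk divides "the number of congenital anomalies associated with any pregnancy outcome by the sum of the number of live births without congenital anomalies" plus all outcomes that involve an anomaly. A loss or termination with an anomaly enters both numerator and denominator. A loss or termination without one enters neither.
- **Stratification (5.3).** "Estimates of risk will also be analyzed as stratified by trimester of exposure".
- **Trimester limits (5.3).** "Trimesters will be defined as < 14 weeks (1st trimester), 14 to 27 weeks (2nd trimester) and" from week 28 onwards for the third.
- **Exposure (5.3).** "Prenatal exposure will be summarized by trimester(s) exposed as well as exposure up to 8 weeks before LMP, dose and regimen". A woman treated in several trimesters can apparently appear in more than one stratum; the text does not say how she is assigned for the comparison.
- **Internal comparison (3.5, 5.1).** If data suffice, "the frequency of congenital malformations among women with first trimester exposure will be compared to women with second and third trimester exposure". Section 5.1 gives the output as a risk estimate with a 95% confidence interval, and its purpose as showing whether risk is increased.

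None of these sections limits the comparison to pregnancies that reached the same gestational age, or treats exposure as changing over time. The review of exposure by gestational week in 5.3 is for individual cases. The limitations in Section 9 discuss external controls but not this point.

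**The concern.** To be classed as exposed in a later trimester, a pregnancy must first survive into it. Affected pregnancies can end early. Section 3.4.2 records terminations for an identified anomaly together with gestational age at outcome, and Section 3.1 prefers first-trimester enrolment, so early endings will be seen. Such a pregnancy adds one case and one denominator unit to the earlier stratum and nothing to the later one. Under the formula, unaffected early losses cannot balance it, because they are not counted.

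The later strata are thus cleared in advance of some affected pregnancies, and first-trimester risk looks higher even if timing of exposure does not matter. This is also the direction that Section 3.5 expects, so an artefact could be read as confirmation. The comparison is the registry's only internal control, and Section 2 says that the findings will be used for counselling.

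**Working it through.** **The plan's own figure.** The protocol gives no number for the internal comparison. Its one computable figure is power above 80% for an 80% increase over 3% (to 5.4%) with 500 women, two-sided alpha 0.05. A one-sample normal approximation gives

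z = [(0.054 − 0.03)√500 − 1.96√(0.03 × 0.97)] / √(0.054 × 0.946) ≈ 0.895, so power is 81.5%.

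The figure reproduces. It concerns the comparison with a fixed background rate, and nothing below depends on it.

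**Inputs**
- p = 0.03 in every stratum (background from Section 5.2; no effect of timing).
- Trimester boundaries at weeks 14 and 28 (Section 5.3).
- f = share of counted anomaly-affected pregnancies that end before the boundary. The protocol gives no value. Assumed ranges: 5-15% before week 14 and 20-40% before week 28.
- One counted anomaly per affected pregnancy (simplification).

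**Overlapping strata.** Every pregnancy exposed in the first trimester counts there, and those still treated later also count in the later stratum.

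- First-trimester risk = p
- Later-stratum risk = p(1 − f) / [p(1 − f) + (1 − p)]

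For f = 0.10: 0.027 / (0.027 + 0.97) = 2.71%, and 3.00 / 2.71 = 1.11.

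| Boundary | f (assumed) | First-trimester risk | Later-stratum risk | Spurious ratio |
|---|---|---|---|---|
| any | 0% | 3.00% | 3.00% | 1.00 |
| Week 14 | 5% | 3.00% | 2.85% | 1.05 |
| Week 14 | 10% | 3.00% | 2.71% | 1.11 |
| Week 14 | 15% | 3.00% | 2.56% | 1.17 |
| Week 28 | 20% | 3.00% | 2.41% | 1.24 |
| Week 28 | 30% | 3.00% | 2.12% | 1.42 |
| Week 28 | 40% | 3.00% | 1.82% | 1.65 |

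**Mutually exclusive strata.** Let c be the share of pregnancies reaching week 14 that are still treated then (assumed 10-50%). The risk with first-trimester exposure only is

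p[1 − (1 − f)c] / {p[1 − (1 − f)c] + (1 − p)(1 − c)}.

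For f = 0.10 and c = 0.30: 0.0219 / (0.0219 + 0.679) = 3.12%, against 2.71%, ratio 1.15. Over c = 10-50% the ratio is 1.06-1.10 at f = 5% and 1.12-1.22 at f = 10%. Separating the groups therefore does not remove the bias.

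**Common landmark.** If both groups include only pregnancies ongoing at week 14, both show the later-stratum risk in the table (2.85%, 2.71% or 2.56%) and the ratio returns to 1.00. The same holds at week 28 (2.41%, 2.12% or 1.82%).

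**The case against.** The strongest objection is that the at-risk set for a trimester comparison is detail for the statistical analysis plan, which is not at hand, and that no sentence rules out a gestational restriction. This does not dispose of the point. The protocol itself fixes the formula, the trimester limits and the stratification, and following them as written gives the tilted contrast.

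Other parts of the objection stand and limit the point:

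- **Terminations after the mid-second-trimester scan.** A reader might infer that these also fall only in the first-trimester stratum. They need not. That assessment is at 21 ± 2 weeks, so a woman still treated after week 14 is already second-trimester exposed. Such a case is lost only to the third-trimester stratum.
- **Chromosomal and genetic disorders.** Section 3.3 does not record them as major malformations, and 5.3 evaluates them separately. Many early endings after prenatal testing may therefore lie outside the count, which favours the low end of the week-14 range.
- **Which ratio applies.** Sections 3.5 and 5.1 can be read as comparing first-trimester exposure with one pooled later group. Entry to that group is at week 14, so the smaller range applies. The larger range needs a separate third-trimester contrast.
- **Precision.** At 3%, 500 women give about 15 cases. With an assumed 400/100 split (12 and 3 cases), the 95% confidence interval around a ratio of 1 is roughly 0.29-3.5. A shift of 1.05-1.17 is small beside that, so the documents do not support calling the estimate uninterpretable.
- **Restricting to survivors has its own bias.** If first-trimester exposure causes anomalies that end pregnancies early, a landmark analysis removes that effect. It should not replace the unrestricted estimate.

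**Conclusion.** The point holds as a directional bias in a stated analysis rule. As written, the internal comparison is tilted towards higher first-trimester risk whenever any counted anomaly ends a pregnancy before the later stratum's entry week, and no other text corrects this.

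The direction is fixed; the size rests on assumed early-ending shares. Against second-trimester or pooled later exposure, the spurious ratio is about 1.05-1.17 with overlapping strata, more plausibly near the low end. Against third-trimester exposure alone it is about 1.24-1.65.

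A reader might go further and infer that the registry's main result is biased, or that any first-trimester excess would be an artefact. The documents support neither. The primary objective is the overall frequency, the main comparison is external, and both are untouched by this mechanism. The internal comparison is additional and conditional on enough data, and a true first-trimester effect could coexist with the bias.

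**What to change.** In Sections 5.1 and 5.3:

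1. Beside the unrestricted trimester estimates, report a comparison limited to pregnancies ongoing at a common landmark: week 14 for first-trimester versus later exposure, and week 28 for any separate third-trimester contrast.
2. In that comparison, class exposure by whether treatment had stopped before the landmark or was continuing at it. Classing by exposure after the landmark would let part of the survival advantage back in.
3. List anomalies in pregnancies that ended before the landmark separately, by exposure.
4. State that the unrestricted contrast is subject to survival bias.
5. Keep the any-outcome numerator for the overall rate and the external comparison.

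The cost is analysis wording only, because dosing dates (Section 3.4.1) and gestational age at outcome (Sections 3.4.2 and 3.4.3) are already collected. The downside is that the restricted analysis has fewer cases and can miss an exposure effect that ends pregnancies early, which is why both analyses should be reported.
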